1.8. Pharmacokinetics and Metabolism in Healthy Volunteers

Fexinidazole is well absorbed by the oral route, and rapidly metabolised to sulfoxide (M1) and sulfone (M2), which account for the largest proportion of drug exposure, regardless of the dose used. Elimination of the second active metabolite is a slow process. C_{max} values for both fexinidazole and M1 are reached in 3 to 6 hours, while M2 levels peak at approximately 24 hours. The mean elimination half-life of fexinidazole and M1 is approximately 10 hours versus approximately 24 hours for M2.

Plasma levels of fexinidazole, M1 and M2 increase in a non-dose-proportional manner with no major changes in their pharmacokinetic profiles.

Urinary excretion of unchanged fexinidazole, M1 and M2 is very low. Fexinidazole, M1 and M2 together account for only 3% of the total dose.

The effects of concomitant intake of food were assessed in two separate studies. In the first study, administration after a standard high-fat meal (FDA recommended) was compared to administration under fasting conditions, and in the second study, two different field meals, i.e. Plumpy'Nut^{®1} and a traditional meal of rice and beans, were compared to administration under fasting conditions. The observed bioavailability of fexinidazole, M1 and M2 was multiplied by approximately 4-fold with the high-fat meal, and by 2.5- to 3.0-fold with the two field meals (15).

1.9. Choice of Regimen and Dose

All pharmacokinetic data from the first-in-man study were incorporated into a PK model simulating several regimens using different doses in order to calculate the optimal exposure. The primary objective was to achieve exposure in the brain at least twice as high as the minimum inhibitory concentration (MIC) for M2, and the secondary objective was to shorten the duration of treatment to 10 days in order to avoid exposure-related increases in liver enzymes. The food effect was used to maximise exposure over a short period of time and to reduce the dose.

¹ Peanut-based paste in a plastic wrapper for treatment of severe acute malnutrition, easily available in the field.

The analysis came out in favour of using a once-daily dosing regimen after the main meal, starting with a loading dose for 4 days followed by a maintenance dose for 6 days.

This regimen was tested in a second study (49) conducted in healthy subjects who received a single daily dose for 10 days after a main meal of rice, beans and oil. The study population was divided into two cohorts: Cohort 1 received 1800 mg (from D1 to D4) and 1200 mg (from D5 to D10), Cohort 2 received 2400 mg (from D1 to D4) and 1200 mg (from D5 to D10) in a sequential and ascending manner. The first dose was well tolerated overall with only a few gastrointestinal adverse events and headaches, however the second dose had to be stopped due to nausea, vomiting and prolonged anxiety.

On the basis of the plasma concentrations with the first regimen (1800 mg for 4 days followed by 1200 mg for 6 days), it would appear that CSF concentrations compatible with the objective of treatment of late-stage HAT will be achieved. The predicted concentration of the M2 metabolite (fexinidazole sulfone) in the CSF indeed corresponds to more than twice the MIC from Day 2 to Day 10, and more than three times the MIC from Day 4 to Day 6. The prediction of the CSF concentration is based on a free fraction of 0.4 for M2, as measured in the DNDiFEX002 study.

No clinically significant laboratory abnormalities were observed with the first regimen.

Thus, the best tolerated regimen that consistently yielded plasma concentrations within the target range, as well as CSF concentrations within the predicted range, was 1800 mg (3 tablets) once daily for 4 days followed by 1200 mg (2 tablets) once daily for 6 days (15). This dosing regimen was therefore chosen for the phase-II/III study.

The preclinical and clinical data summarised above support the rationale for conducting a study with fexinidazole in patients with late-stage HAT.

1.10. Rationale for the Study Design

Conducting clinical studies in patients with HAT entails several specific difficulties including the need to perform repeated lumbar punctures to confirm diagnosis and cure, the long post-treatment follow-up required to confirm cure (18 months in comparative studies, as recommended by WHO experts in 2004, 54), the lack of a validated early surrogate marker for cure and the extreme poverty of the patients, who live in remote areas with no access to healthcare infrastructures. Given the scarcity of patients and of resources, as well as the lengthy follow-up required, it was decided that a single phase-II/III pivotal study would be performed. NECT was recently shown to be the most effective therapy currently available (43), and was chosen as the reference treatment since it was the latest

treatment to be added to the List of Essential Medicines and is widely recommended by the National HAT Control Programmes.

In order to collect as much safety data on fexinidazole as possible, and considering that the data would come from only one study, an unbalanced randomisation ratio of 2:1 was chosen in order to increase the number of patients exposed to fexinidazole in the study.

A double-blind double-dummy study design was deemed to be too complex and unethical, and could have compromised the study feasibility. Bias in patient selection and treatment allocation will be avoided using centralised randomisation. No one in the Sponsor's team will have access to the randomisation codes as this information will not be visible in the electronic case report form (e-CRF). Only the monitoring team will have access to unblinded data.

An interim analysis of the primary objective will be conducted by a statistician independent of the statistician in charge of the study. If the result of this analysis is not significant, no further analyses will be carried out.

If the interim analysis of the primary objective is significant, it will be validated by the study statistician, who will then be responsible for conducting all the other interim analyses required. The study statistician will no longer be able to participate in decisions taken based on subsequent blinded data reviews or in any amendments introduced after the interim primary analysis. The patient's initial code will not appear in individual data listings. A new ID code will be assigned by the statistician. The blind will be maintained in the Sponsor's team, with the exception of the person in charge of Pharmacovigilance for the Sponsor. This person will be responsible for checking the listings.

1.11. Target Population

Patients with late-stage HAT, 15 years of age and older, will be included in the study.

Based on epidemiological data, patients 15 years of age and older account for approximately 77% of the overall population treated for HAT. From a clinical standpoint, adolescents between 15 and 17 years of age are considered to be physiologically mature, particularly as concerns hepatic and renal maturation. Thus, the PK profiles of fexinidazole and its two main active metabolites are not expected to differ in this age group as compared to patients over 18 years of age.

By including adolescents between 15 and 17 years of age, the efficacy and safety of fexinidazole will be assessed in the same population as that used for the study on NECT (43). This point is of particular relevance since, in a non-inferiority study, it is especially important to closely adhere to the design of the historical studies, in accordance with European directives (11). In addition, the minimum age of patients included in other studies on HAT conducted in Africa was also 15 years

of age, such as the phase-II study on pafuramide maleate (or DB289), a compound developed for the treatment of early-stage HAT (25).

In the on-going NECT-Field study assessing the clinical safety, feasibility of use and efficacy of NECT under real-life conditions (16), 3.7% of the patients included are between 15 and 17 years of age. As in prior clinical studies on HAT, the inclusion of adolescents over 15 years of age with the adult population will help facilitate recruitment of patients with late-stage HAT and, assuming that fexinidazole proves to be effective, will allow for immediate recommendation of its use in adolescents.

Moreover, adolescents over 15 years of age are well able to understand the study objectives and constraints, and can give their assent to participation in the study (see Section 14 Ethics; p 77).

2. Study Objectives and Endpoints

2.1. Objectives

2.1.1. Overall Objective

The overall objective of the study is to assess the efficacy and safety of an oral regimen of fexinidazole, once daily for 10 days, as compared to NECT in the treatment of late-stage sleeping sickness due to *T. b. gambiense*.

2.1.2. Primary Objective

 To demonstrate that the success rate at 18 months after the end of treatment (EOT) is in favour of fexinidazole, or that the difference as compared to the success rate with NECT is acceptable.

2.1.3. Secondary Objectives

- To compare the time course of the failure rate with fexinidazole and NECT from the EOT visit to 24 months, i.e. the end of the long-term follow-up period.
- To compare the safety of fexinidazole with that of NECT in the treatment of late-stage sleeping sickness due to *T. b. gambiense*.
- To assess plasma and CSF concentrations of fexinidazole and its metabolites in all patients who receive fexinidazole, and to investigate the correlation between the concentration and the efficacy and safety of fexinidazole in patients with late-stage sleeping sickness due to *T. b. gambiense*.
- To compare the pharmacodynamic impact of fexinidazole and of NECT on QT/QTcF interval, as measured on ECG.

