Study Objectives	 The objective of the study is to assess the efficacy and safety of an oral regimen of fexinidazole, once daily for 10 days, as compared to NECT in the treatment of late-stage sleeping sickness due to T.b. gambiense. Primary Objective To demonstrate that the success rate at 18 months after the
	end of treatment is in favour of fexinidazole, or that the difference as compared to the success rate with NECT is acceptable. Secondary Objective
	 To compare the time course of the failure rate with fexinidazole and NECT from the end of treatment visit to 24 months.

1

Г

	 To compare the safety of fexinidazole with that of NECT in the treatment of late-stage sleeping sickness due to T. b. gambiense. To assess concentrations of fexinidazole and its metabolites in the plasma and cerebrospinal fluid, and the correlations
	between the concentration and the efficacy and safety of fexinidazole.
	 To compare the pharmacodynamic impact of fexinidazole and of NECT on QT/QTcF interval.
	Exploratory Objectives
	 To validate the predictive value of three logistic models for treatment success at 18 months.
	 To compare the efficacy of fexinidazole to that of melarsoprol, eflornithine and NECT using historical data as comparators.
Primary	Efficacy
Endpoint	Outcome, i.e. either success or failure, of treatment assessed at the test-of-cure visit, 18 months after the end of treatment, based on adapted WHO criteria (55).
Secondary	Efficacy
Endpoints	Outcome, i.e. either success or failure, of treatment assessed at each visit between the end of treatment and 24 months.
	Safety
	Occurrence of adverse events, including laboratory or ECG abnormalities during the observation period, i.e. from D1 to D8, and occurrence of serious adverse events between the first treatment intake and the end of the follow-up period, i.e. 18 months. Long-term safety will be assessed up to 24 months.
	Pharmacokinetics
	Pharmacokinetic analyses will be performed on all patients in the fexinidazole group using serial dry blood spots and one dry cerebrospinal fluid spot.
	Electrocardiogram (ECG)
	Categories of QT/QTcF and changes at various timepoints.
Exploratory	Surrogate Efficacy Endpoint
Endpoint	The surrogate endpoint is the actual or predicted outcome (using logistic models, if the outcome is missing) at 18 months, based on the outcome at the last visit that took place at 6 months or later

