Patients living in an area of armed conflict and who, according to those close to him/her and/or inhabitants of the village, fled the area for a safer region and for whom no post-treatment data are available after several attempts to obtain such information, will not be taken into account in the primary efficacy analysis or in the interim analysis, but will be included in the safety analysis.

Success at 18 months is defined as:

- Patient cured, i.e.
 - o patient alive,
 - o AND no evidence of trypanosomes in any bodily fluid,
 - AND CSF WBC $\leq 20/\mu$ L.

OR

- Patient probably cured, i.e.
 - o no parasites in blood or lymph,
 - AND refusal to undergo lumbar puncture, OR whose CSF sample is haemorrhagic but with no trypanosomes,
 - AND whose clinical status is satisfactory, i.e. with no clinical signs or symptoms, OR whose clinical status is unlikely to be related to HAT.

Failure at 18 months is defined as:

- Patient relapsed, i.e.
 - o evidence of trypanosomes in any bodily fluid,

OR

- Patient probably relapsed, i.e.
 - o Either no evidence of trypanosomes in any bodily fluid,
 - AND CSF WBC > 20/µL,
 - AND whose WBC cannot be explained by a disease other than HAT,
 - o Or no evidence of parasites in the blood or lymph,
 - AND refusal to undergo lumbar puncture, OR whose CSF sample is haemorrhagic but with no trypanosomes,
 - AND who, in the opinion of the Investigator, requires rescue treatment because of marked deterioration in his/her clinical status that is unlikely to be related to a disease other than HAT,
 - Or patient who refuses lumbar puncture at 18 months and in whom the outcome had already been assessed as unfavourable at an earlier time (see Table 1 – Definitions of Early Efficacy Endpoints; p Error! Bookmark not defined.),
 - Or withdrawal from the study due to probable relapse at any time earlier than 18 months (see Table 1 – Definitions of Early Efficacy Endpoints; p Error! Bookmark not defined.)
- Or death, whatever the cause,
- Or lost to follow-up,

Patients living in an area of armed conflict and who, according to those close to him/her and/or inhabitants of the village, fled the area for a safer region and for whom no post-treatment data are available after several attempts to obtain such information, will not be taken into account in the primary efficacy analysis or in the interim analysis, but will be included in the safety analysis.

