12 months	12 months ± 4 weeks	n =195	 Patient alive with no evidence of trypanosomes in any bodily fluid and CSF WBC ≤ 20/µL No evidence of trypanosomes in blood or lymph and refusal to undergo lumbar puncture or whose CSF sample is haemorrhagic but with no trypanosomes and whose clinical status is satisfactory, i.e. with no clinical signs or symptoms, or whose clinical status is unlikely to be related to HAT No lumbar puncture at 12 months, but one at 6 months with CSF WBC ≤ 5/µL 	 No evidence of trypanosomes in any bodily fluid and CSF WBC > 20/µL and whose WBC cannot be explained by a disease other than HAT No evidence of trypanosomes in blood or lymph and refusal to undergo lumbar puncture or whose CSF sample is haemorrhagic but with no trypanosomes and intake of rescue treatment Refusal to undergo lumbar puncture at 12 months and outcome assessed as unfavourable at previous visits Withdrawal from study due to probable relapse at a previous visit No lumbar puncture at 12 months, but one at 6 months with CSF WBC > 5/µL No lumbar puncture at 12 or 6 months 	• Evidence of trypanosomes in any bodily fluid

For statistical purposes, an unfavourable outcome is any situation that does not fulfil the criteria for favourable outcome in Table 1.

Late Efficacy Endpoint (24 months)

The same definitions as those for the primary endpoint will be used. The ideal timing of this visit should be 24 months \pm 4 weeks after EOT.

Surrogate Efficacy Endpoint

The surrogate endpoint is the actual or predicted outcome (if the outcome is missing) at 18 months, based on the outcome at the last visit that took place at 6 months or later, and for which data are available.

The actual outcome, i.e. success or failure, is the same as that defined in the primary endpoint.

The predicted outcome at 18 months is obtained based on logistic models using CSF WBC at baseline, 6 months and/or 12 months, age and sex.

Unlike the primary endpoint, the surrogate endpoint is used to estimate the success rate in the final analysis, i.e. sensitivity analysis of the primary analysis.

In the final analysis, the surrogate endpoint may be much more accurate than the primary endpoint if the predictive value is as good as the results obtained in the set of patients used to construct the models (see Section 9.2 Handling of Missing Values and Lost to Follow-up; p 58).

Safety Endpoints

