If the analysis of the primary efficacy endpoint for the interim analysis proves not to be significant, no other analyses will be performed and the blind will be maintained for the study statistician and the person in charge of preparing the CSR until the time of data review for the final analysis.

FAs will be performed by an unblinded independent statistician who is not involved in preparing the study, in the blind review of data or in the final statistical analyses. S/he will provide recommendations to the DSMB/ISC with regard to stopping the study for reasons of futility or to continuing the study. The magnitude of the treatment effect will not be revealed. If the study is allowed to continue, this will signify that efficacy is deemed sufficient from an ethical standpoint, but does

not inform about the study's chances of success. Indeed, the endpoints in the FAs are different from the primary endpoint: not only do the conditions for stopping the study differ from those that define treatment success, but the size of the sample in the FAs is small.

The logistic models will be validated in a fully blinded manner, regardless of the treatment group.

After the data base lock on the primary analysis (18 months data), the sponsor, the data management and the statistician will be unblinded. Once all patients reached their 24 months follow up, a sensitivity analysis could be performed on request.

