6.4.3. At the 6, 12 and 18-month Follow-up Visits

- Physical examination, HAT symptoms since the previous visit, neurological assessment including signs and symptoms of HAT
- Testing for *T.b. gambiense* in blood and lymph for diagnosis of potential relapse

- CSF sampling to test for potential relapse, with WBC count and testing for trypanosomes (Fuchs-Rosenthal/Fast Read 102® counting chamber, MSC with INRB kits)
- Additional safety assessments such as ECG, haematology, biochemistry or urine tests may be performed at the discretion of the Investigator.

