6.4.4. At the 24-month Follow-up Visit

- Physical examination, HAT symptoms since hospital discharge, neurological assessment including signs and symptoms of HAT
- Testing for *T.b. gambiense* if relapse is suspected or if required according to current local standard of care.
- Additional safety assessments such as ECG, haematology, biochemistry or urine tests may be performed at the discretion of the Investigator

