Appendix 4 - Tables

Table 4 – Schedule of Study Procedures

Protocol-planned procedures and forms to be completed	Pre-screening and Screening	Baseline	e Treatment period										End-of-Treatment Visit until End-of- Hospitalisation Visit			Follow-up period (months)
Timepoint	D-15 to D-1	D-4 to D- 1	D1	D2	D3	D4	D5	D6	D7	D8	D9	D10	D11	D12	D13-D18	Week 9 ³ 3 – 6 – 12 – 18 -24 months
Detection of parasite in blood and/or lymph	Х												х			х
Lumbar puncture (parasite and white blood cells in CSF)	x												х			x ¹
Informed consent (before any additional medicines or study-specific procedures)	×	Check														
Pretreatment of helminthiasis (+ 3-day recovery period)	x															
Rapid diagnostic test and/or thick blood smear for malaria	Х															
Pretreatment of malaria if necessary (+ 3-day recovery period)	x															
Karnofsky score	Х	Check														х
Safety ECG	Х	Check														
Safety ECG (fexinidazole group only)				х	х	х										
Urine pregnancy test		х													х	x (only at 3 months)
Inclusion and exclusion criteria	Х	х														
Randomisation		х														
Demographic data	Х															
Medical history	Х															х
Signs and symptoms of HAT		х													х	х
Vital signs	Х	х					х			х			х		х	х
Physical examination		х					х			х			х		х	х
Neurological examination		х					х			х			х		х	х
Haematology and biochemistry	Х	х					х			х			х			x (only at Week 9)
Haematocrit ²	Х															
Urine analysis	Х	х											х			

¹ Except for 3-month follow-up visit unless the patient presents with clinical symptoms or signs of HAT.

² Only for patients at sites where PK sampling is performed.

³ Only at Week 9 after D1, perform sampling for haematology and biochemistry, physical examination and neurological examination.

Protocol-planned procedures and forms to be completed	Pre- screening and Screening	Baseline		Treatment period						End-of-Treatment Visit until End-of-Hospitalisation Visit			Follow-up period (months)			
Timepoint	D-15 to D-1	D-4 to D-1	D1	D2	D3	D4	D5	D6	D7	D8	D9	D10	D11 (EOT)	D12	D13-D18	Week 9 3 – 6 – 12 – 18 -24 months
Triplicate ECGs –fexinidazole group		x				x D4H4 D4H23						x D10H2-H3				
Triplicate ECGs – NECT group		x							x D7H2- H3			x D10H2-H3				
Administration of fexinidazole			х	х	х	х	х	х	х	х	х	х				
Administration of NECT			х	х	х	х	х	х	х	х	х	х				
Treatment-related adverse events			х	х	х	х	х	х	х	х	х	х	х	х	х	

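### The protocol contradicts itself on what is examined at month 24, so the month-18-to-24 part of the failure-rate comparison is selectively measured

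*Protocol*

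**What the plan says.** - **Objective.** Section 2.1.3 of the Protocol lists first "To compare the time course of the failure rate with fexinidazole and NECT from the EOT visit to 24 months". The Protocol Summary gives the matching endpoint: "Outcome, i.e. either success or failure, of treatment assessed at each visit between the end of treatment and 24 months".
- **Definition at month 24.** Section 2.2.2, under the late efficacy endpoint, states: "The same definitions as those for the primary endpoint will be used". In section 2.2.1, a cured patient is alive, has no trypanosomes in any fluid and has a CSF white cell count of at most 20/µL. A probably cured patient has negative blood and lymph, a satisfactory clinical status, and also meets this condition: "AND refusal to undergo lumbar puncture, OR whose CSF sample is haemorrhagic but with no trypanosomes".
- **Visit text.** Section 6.4.4 has parasite testing at month 24 "if relapse is suspected or if required according to current local standard of care" and lists no CSF count. For months 6, 12 and 18, section 6.4.3 schedules "CSF sampling to test for potential relapse, with WBC count and testing for trypanosomes" without such a condition.
- **Schedule table.** Table 4 (Appendix 4) marks blood/lymph parasitology and lumbar puncture in the follow-up column that includes month 24. The footnote to the puncture row reads "Except for 3-month follow-up visit unless the patient presents with clinical symptoms or signs of HAT". A separate footnote limits the Week 9 visit. Neither exempts month 24.
- **Clinical classification.** Table 2 (section 5.9) puts months 18 and 24 in one row and classifies both by CSF white cell count.

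**The concern.** Sites have two incompatible instructions for the same visit, and the endpoint definition works under only one of them. A site following Table 4 produces a month-24 outcome that the primary definition can classify. A site following 6.4.4 leaves most well patients without the data that the definition needs.

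Three things are at stake:

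- **Who is measured.** Under 6.4.4, the patients with a classifiable month-24 outcome are mainly those whom someone suspected of relapse.
- **Who decides.** The trial is open-label (section 5.7), so suspicion is formed by investigators who know the treatment. Local standard of care is the other trigger. Detection can therefore differ by arm and by centre.
- **What is missed.** A relapse visible only in the CSF after month 18 would go unseen in an untested patient. The protocol itself allows for relapses in that window, in the section 9.2 footnote on the logistic models.

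**Working it through.** The plan states no figure to reproduce. The check sets the passages side by side and follows one patient through them.

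**Step 1: a well patient at month 24 under 6.4.4.** The patient attends, is alive and has no signs of HAT. Relapse is not suspected and local care requires no test. No puncture is done, and none is refused because none is offered. Against the section 2.2.1 definitions:

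| Category | Needs | Met? |
|---|---|---|
| Cured | No trypanosomes, CSF count ≤ 20/µL | No: no CSF result |
| Probably cured | Negative blood/lymph, and puncture refused or sample haemorrhagic | No: neither refused nor haemorrhagic, and blood/lymph not tested |
| Relapsed | Trypanosomes found | No |
| Probably relapsed | CSF count > 20/µL; or need for rescue, or an earlier unfavourable outcome, with the puncture refused (for rescue, also a haemorrhagic sample); or earlier withdrawal for probable relapse | No |
| Death or lost to follow-up | – | No: the patient was seen alive |

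The patient has no outcome.

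**Step 2: what the analysis does with a missing month-24 outcome.** Section 9.2 assigns the third method, no imputation, to the Kaplan-Meier analysis. Its back-fill rule needs a later visit, and there is none after month 24. The method censors at the first missing outcome when all later ones are missing. Section 9.8.3 also imputes nothing and censors patients lost to follow-up just after the last available assessment. For the repeated-measures logistic model, it fills only intermediate gaps lying between favourable outcomes, and month 24 is not intermediate. Handled as 9.8.3 handles losses, the untested well patient leaves the risk set after month 18. The suspected, tested patient stays.

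**Step 3: how much this can move the estimate.** The documents do not give the number tested at month 24. Assume 220 fexinidazole patients event-free after month 18, of whom 4 are suspected and tested at month 24 and 3 have relapsed. Conditional failure between months 18 and 24 = relapses / patients at risk at month 24.

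- Untested patients censored just after month 18: 3 / 4 = 75%.
- Untested patients kept at risk to month 24: 3 / 220 = 1.4%.

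The relapses are the same and only the handling differs. The second figure may also be too low, because relapses visible only in the CSF among the 216 untested patients (220 − 4) are not counted. The first reading is the one nearest to 9.8.3. The second would follow if censoring at the first missing outcome in 9.2 were dated to the month-24 visit itself. The text does not settle this for a patient who attends but is not examined.

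**Step 4: link to the primary endpoint.** Section 9.8.1 counts a patient who refuses the month-18 puncture as a success if there are no signs of HAT and the latest assessment was favourable, unless signs of relapse appear on any assessment up to 24 months. What is examined at month 24 can therefore change some month-18 outcomes. The documents do not give the number of such refusers. Section 6.4.4 keeps the physical and neurological examinations, so the exposure is limited to relapses that only a test would show.

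**The case against.** The strongest reply is that this is a schedule inconsistency at a visit of minor importance. Section 5.3 treats participation as complete at month 18 and explains the month-24 visit by national programme recommendations. The only Kaplan-Meier difference named in 9.8.3 is at 18 months. Mixed ascertainment is also not peculiar to month 24: puncture refusers and haemorrhagic samples count as successes at months 12 and 18 on clinical grounds, and month 3 has a puncture only on suspicion.

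Part of this stands. The primary test, interim analysis and futility rules are not in question, apart from the narrow link in section 9.8.1. But the objective and the Summary endpoint explicitly run to month 24. At month 3, the definition in Table 1 is written for a visit without a routine puncture, and a missed relapse can still be found at month 6. At month 24 the definition is not adapted, and no planned visit follows.

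A reader might also infer more than the documents support:

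- *That the month-18-to-24 question cannot be answered.* Table 4 schedules the tests and Table 2 uses the CSF count there, although Table 2 is stated not to be used directly for statistics. Even under 6.4.4, deaths, rescue treatment, tested suspicions and locally required tests are captured.
- *That nearly all untested patients become failures.* The no-imputation and censoring rules of 9.2 and 9.8.3 say otherwise. The rule that whatever is not favourable is unfavourable belongs to Table 1, which stops at 12 months.
- *That the month-24 report is optional.* Section 5.7 says "Once all patients reached their 24 months follow up, a sensitivity analysis could be performed on request", which concerns a sensitivity analysis. Table 6 already schedules a follow-up report.

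**Conclusion.** The point holds as an internal contradiction with an analytic consequence. Section 6.4.4 disagrees with Table 4 and does not supply what the 2.2.2 definition needs. Where 6.4.4 is followed, well, untested patients have no outcome category, and the stated missing-data rules tend to remove them while keeping those tested on suspicion. The final segment of the failure curve is then selectively measured, open to influence from knowledge of treatment, and not on the same footing as months 6 to 18.

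The size cannot be fixed from the documents. It depends on how many of the 390 patients are seen at month 24 without being tested, and on how censoring is dated. The range of 1.4% to 75% rests on assumed counts and shows sensitivity to the rule; it is not a forecast. The comparison from end of treatment to month 18 is unaffected, except for puncture refusers under the section 9.8.1 rule.

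**What to change.** 1. Reconcile section 6.4.4, Table 4, Table 2 and the late-endpoint definition in 2.2.2, so that they describe one month-24 examination. Which schedule is right is a clinical matter for the sponsor and investigators; this review takes no position on it.
2. State in 9.2 and 9.8.3 how a patient who attends month 24 but has no parasitology or CSF count is classified, and at what time that patient is censored. This is needed under either schedule.
3. If month-24 testing stays suspicion-driven, end the formal between-arm time-course comparison at month 18 (2.1.3, Summary, 9.8.3). Replace the carried-over definition with a descriptive month-24 tabulation by arm: relapse detected, none detected clinically, CSF not examined.
4. State whether month-24 findings can still overturn a month-18 probable cure under 9.8.1, and from which examinations.

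Cost: wording changes only and no extra patients. If item 3 applies, the comparative claim is six months shorter (24 − 18).
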